ELO will be given on cycle days 1 and 15.

Dexamethasone as in cycles 1-2.

Cycles 9 -

CAR, ELO and Dex will be given on days 1 and 15 from cycle 9 until relapse or progression or excess toxicity.

Duration of Study:

Expected duration of treatment:

- patient recruitment 24 months
- primary endpoint (ORR) together with the relevant secondary endpoints will be assessed after the minimum follow-up of one year has been reached with the last included patient
- to assess PFS and TTNT all patients will be followed until 4 years after first dose

Helsinki University Hospital Comprehensive Cancer Center Hematology
Clinical study protocol NMSG#24/15

LIST OF ABBREVIATIONS AND GLOSSARY OF TERMS

Common abbreviations used in oncology protocols are provided below. Program-specific or protocol-specific abbreviations must be added to this list, and unnecessary abbreviations removed, as applicable. Abbreviations that are retained should not be changed.

Abbreviation	Term
AE	adverse event
AFOS	alkaline phosphatase
ALT, ALAT	alanine aminotransferase
ANC	absolute neutrophil count
API	active pharmaceutical ingredient
ASCO	American Society of Clinical Oncology
ASCT	Autologous stem cell transplantation
ASO-RQ	Allele specific oligonucleotide real-time quantification
AST	aspartate aminotransferase
AUC	area under the plasma concentration versus time curve
AUC _{24 hr}	area under the plasma concentration versus time curve from zero to 24 hours
AUC _{inf}	area under the plasma concentration versus time curve from zero to infinity
AUC _τ	area under the plasma concentration versus time curve from zero to next dose
BID	bis in die; twice a day
BM	bone marrow
BSA	body surface area
BUN	blood urea nitrogen
BZM	Bortezomib
CBC	complete blood count
CL	clearance, IV dosing
CL _p	plasma clearance
CL _{Total}	total clearance
C _{max}	single-dose maximum (peak) concentration
CNS	central nervous system
CR	complete remission
CrCl	Creatinine Clearance
CRO	Clinical trial research organization
CRP	C-reactive protein
CT	computed tomography

Helsinki University Hospital Comprehensive Cancer Center Hematology
Clinical study protocol NMSG#24/15

Abbreviation	Term
CY	Cyclophosphamide
CYP	cytochrome P ₄₅₀
DDI	drug-drug interaction
DLT	dose-limiting toxicity
DME	drug metabolizing enzymes
DNA	deoxyribonucleic acid
DSRT	Drug sensitivity and resistance testing
ECG	Electrocardiogram
ECOG	Eastern Cooperative Oncology Group
eCRF	electronic case report form
ELISA	enzyme-linked immunosorbent assay

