TTNT	Time to next treatment
UK	United Kingdom
ULN	upper limit of the normal range
US	United States
VGPR	Very good partial remission
VTE	Venous thromboembolism
WBC	white blood cell
WHO	World Health Organization

[figure not shown]
Helsinki University Hospital Comprehensive Cancer Center Hematology
Clinical study protocol NMSG#24/15

Table 1. Schedule of study investigations

	Screening	Cycles 1- until end of study, D1 (lab within 5 days before)	Cycles 1-8, D8 D15, D22* (lab within 3 days)	Cycles 1-8 D15	Cycles 9-, D15 until end of study (lab in 3days)	End of study
Medical history	X					
Physical examination + neurool.evaluation	X	X	X**			X
Vital signs	X	X	X*		X	X
Hematology	X	X				X
Immunochemistry	X	X				X
Blood chemistry	X	X				X
Pvk+neut+tromb, K,Na,krea,alat, afos,bil (safety lab*)			X*		X	
Safety assessment, AEs	X	X	X*		X	X
BM aspiration+ 8-color EuroFlow	X		X (when VGPR has achieved, repeated if VGPR/CR and after 1 year if VGPR/CR)			
Bm-MM-FISH	X					
Bone imaging	X					
ECG (a)	X					
Thorax x-ray	X					
Cardiac ECHO	X					
Biobank	X			In CR and at relapse		
Samples to FIMM in Finland	Finland			Bm + blood at relapse		
Pregnancy test (b)	X	X (b)				
Quality of Life		X		X		X

a) ECG in C1-2, D1, thereafter if clinically needed. b) Pregnancy testing must be performed at the beginning of each 28-day cycle and at the end of study visit, applying to women of childbearing potential. * Vital signs not needed on D22 and after C2 Safety lab and AEs on D22 if clinically needed. ** Physical examination if needed due to clinical symptoms.

Table 2. Study schema

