6.6 Bone marrow assessment

Bone marrow samples at entry for multiparameter flow cytometry (MFC) (if it has not taken at diagnosis) and if VGPR/CR has been achieved and annually if response has been maintained

Bone marrow samples at entry for FISH analysis to investigate del17p and screening of translocations 4;14, 14;16 and 14;20, +1q, except the patient already has had these aberrations.

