9.1 ENDPOINT DEFINITIONS

Primary endpoint of this study is overall response rate

Secondary endpoints are

- Complete remission (CR) rate
- Quality of response (proportion of MRD negativity in patients with at least VGPR)
- Duration of responses including MRD negativity
- Progression-free survival (PFS)
- Time to next treatment (TTNT)
- Safety (Adverse events)

Minimal residual disease (MRD) will be assessed by 8-colour EuroFlow multiparameter flow cytometry if at least VGPR has been achieved.

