9.2 STATISTICAL AND EFFICACY ANALYSES

Statistical analyses will be performed on intention-to-treat and on per-protocol-treated principle. Patients who have been included in the study but been withdrawn before any study drug administration are not included in analyses. Safety and efficacy analyses will be done for all patients who have received at least a single dose of study drug. Any spurious data will be abandoned. Missing

Helsinki University Hospital Comprehensive Cancer Center Hematology
Clinical study protocol NMSG#24/15

data will be handling as missing data not with replacing it with a median parameter number.

Efficacy analyses will be done using International Myeloma Working Group response criteria (Appendix 5). Response will be assessed before each cycle. Progression will be assessed using IMWG criteria for progressive disease.

For classification the adverse events NCI CTCAE version 4.0 will be used. Threshold for safety of this CAR-ELO-Dex combination is considered to be less than 70% of grade ≥ 3 non-hematological adverse events.

Efficacy, safety and QoL analysis will be performed when last patient in has been treated for two years in the study. Kaplan-Meier method will be used to estimate the time to event analyses. The PFS, TTNT and duration of response will be calculated from the start of the first dose of study drug combination.

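### Marrow samples about a year apart make duration of MRD negativity interval-censored, so Kaplan-Meier on detection dates is coarse and generally too long; Table 1 and section 6.6 also disagree on the later samples

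*Protocol*

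**What the plan says.** Section 9.1 lists "Duration of responses including MRD negativity" among the secondary endpoints, separately from the proportion who are MRD-negative. MRD is measured by flow cytometry, and only "if at least VGPR has been achieved".

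Section 9.2 states that the "Kaplan-Meier method will be used to estimate the time to event analyses" and names no other method for durations. On the time origin it says: "The PFS, TTNT and duration of response will be calculated from the start of the first dose of study drug combination". Conventional response is followed much more closely than MRD: "Response will be assessed before each cycle", that is, every 28 days.

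The marrow schedule appears twice. Section 6.6 takes marrow for flow cytometry at entry, then "if VGPR/CR has been achieved and annually if response has been maintained". Table 1 gives, after screening, "when VGPR has achieved, repeated if VGPR/CR and after 1 year if VGPR/CR".

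**The concern.** MRD status can change only when a marrow is taken. Once the response-triggered sample has been read as negative, the next dated look is about a year away. A patient who turns positive one month later would be recorded as positive at that next marrow, some 11 months late. Such data are interval-censored: all that is known is that the loss fell between the last negative and the first positive sample. Kaplan-Meier applied to the date of detection treats the end of each interval as the event time.

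Two further features add to this. Section 6.6 makes the later marrows conditional on maintained response, so patients who progress first may never have a positive marrow. And if Table 1 governs, no MRD marrow is dated after the 1-year sample, so a later loss would not be seen in marrow at all. At stake is a duration that partly reflects the sampling calendar and cannot safely be set beside trials that sample at other intervals.

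**Working it through.** **No figure to reproduce.** The protocol gives no expected duration of MRD negativity. Everything about its distribution below is an assumption.

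**The two schedules side by side**

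| | Section 6.6 | Table 1 |
|---|---|---|
| First on-treatment marrow | at VGPR/CR | at VGPR |
| Repeat | none named | yes, undated |
| Later marrow | annually while response lasts | once, after 1 year |
| Dated marrow at 24 and 36 months | yes, if still responding | no |

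Neither says what the year is counted from.

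**Annual marrow alone, clock from the first negative sample.** Let the true time to loss T be exponential with median m, so λ = ln 2 / m. The recorded time is 12 × ⌈T/12⌉. Its mean is 12 / (1 − e^(−12λ)), the true mean is 1/λ, and the mean delay is the difference.

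| True median m (months) | e^(−12λ) | Recorded mean | True mean | Mean delay |
|---|---|---|---|---|
| 6 | 0.250 | 12/0.750 = 16.0 | 8.66 | 7.3 |
| 12 | 0.500 | 12/0.500 = 24.0 | 17.31 | 6.7 |
| 18 | 0.630 | 12/0.370 = 32.4 | 25.97 | 6.5 |
| 24 | 0.707 | 12/0.293 = 41.0 | 34.62 | 6.3 |

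The error in the median is less regular. The share lost by month 12 is 1 − 2^(−12/m). For m = 6 this is 75%, so the recorded median is 12. For m = 18 it is 37% at month 12 and 60% at month 24, so the recorded median is 24. For m = 24 the recorded median is 24, with no error.

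**Variants.** These were simulated with 400,000 draws for each of m = 6, 12, 18 and 24, without administrative censoring.

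| Variant | Mean overstatement (months) |
|---|---|
| Annual marrow, from first negative | 6.3–7.3 |
| Plus the Table 1 repeat, assumed 2–8 months after the first negative | 4.6–5.4 |
| Annual marrow, with progression (checked each cycle; mean lag after loss 6 or 12 months) ending negativity | about 4–5.5 |
| Repeat and progression together (mean lag 12 months) | 3.7–4.2 |
| Annual marrow, with onset also falling between two annual samples | 0.7–2.7; 15–46% of episodes never seen |
| Annual marrow, clock from first dose, first MRD marrow assumed at 2–8 months | about 11–12 |

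In the last row about 5 months, the midpoint of 2–8, comes from the choice of origin (6.3 + 5 = 11.3; 7.3 + 5 = 12.3). Only the rest comes from the sampling interval.

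**The case against.** Section 9.2 does not name MRD duration when it prescribes Kaplan-Meier. Start, end and censoring rules are commonly left to a statistical analysis plan, which is not at hand. That stands: the lack of those definitions is no fault in itself, and the use of Kaplan-Meier here is inferred. But an analysis plan cannot add marrow samples, nor settle a conflict between two schedules that both belong to the protocol.

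A reader might infer that the recorded duration can take only values near 12, 24 or 36 months. The documents do not support this. The only origin given for duration of response is the first dose; with the first MRD marrow at an assumed 2–8 months, none of the simulated values fall within one month of 12, 24, 36 or 48. Table 1 also has an undated repeat, and progression is checked every cycle. If progression ends negativity, 38–64% of values lie near a 12-month multiple; with the repeat as well, 41–50% do.

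The size of the bias is also open to challenge. True medians just below a sampling date give little error in the median, and late detection of onset offsets late detection of loss. Both points stand.

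Finally, the efficacy indicator that the study overview stresses is the proportion with MRD-negative CR, not its duration. The duration concerns only those of 40 patients who reach VGPR and test negative, in a trial that calls itself a pilot.

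**Conclusion.** The point holds in a limited form. On either schedule, loss of MRD negativity can go undetected in marrow for up to about 12 months, so Kaplan-Meier on detection dates is coarse. The bias was upward in every variant examined, with a mean from 0.7 to 7.3 months when counted from the first negative sample. Where in that range it falls depends on whether the repeat is taken, whether progression ends negativity and how late onset is seen. All of these figures rest on assumed exponential loss and assumed timings. A fixed overstatement of 6 to 7 months would be too strong a reading, since it applies only to annual marrow alone.

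The disagreement between Table 1 and section 6.6 needs no assumption. Nor should a reader conclude that the trial's MRD results are unsound in general: the MRD-negative proportion and the primary ORR are untouched.

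**What to change.** 1. In sections 9.1 and 9.2, replace the Kaplan-Meier duration by the proportion of MRD-negative patients whose negativity is sustained at the 1-year marrow. Both schedules already contain that sample. Count progression or death before it as not sustained. Report other missing samples separately, with a sensitivity analysis. Counting every missing sample as a failure would conflict with the rule in section 9.2 that missing data stay missing, and would bias the result downward.
2. If a duration is kept, start it at the first MRD-negative sample, treat the end as interval-censored between the last negative sample and the first positive sample or progression (a Turnbull estimate, for example), and quote no Kaplan-Meier median.
3. Reconcile Table 1 with section 6.6 on when the repeat is taken, whether there is one later marrow or an annual series, and what 1 year is counted from.

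The cost is wording in two sections and one line of Table 1; the sustained-negativity measure needs no new samples. The downside is that no single Kaplan-Meier duration is reported for MRD, and an interval-censored estimate in a subset of 40 patients will be imprecise.

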9.2 STATISTICAL AND EFFICACY ANALYSES

Statistical analyses will be performed on intention-to-treat and on per-protocol-treated principle. Patients who have been included in the study but been withdrawn before any study drug administration are not included in analyses. Safety and efficacy analyses will be done for all patients who have received at least a single dose of study drug. Any spurious data will be abandoned. Missing

Helsinki University Hospital Comprehensive Cancer Center Hematology
Clinical study protocol NMSG#24/15

data will be handling as missing data not with replacing it with a median parameter number.

Efficacy analyses will be done using International Myeloma Working Group response criteria (Appendix 5). Response will be assessed before each cycle. Progression will be assessed using IMWG criteria for progressive disease.

For classification the adverse events NCI CTCAE version 4.0 will be used. Threshold for safety of this CAR-ELO-Dex combination is considered to be less than 70% of grade ≥ 3 non-hematological adverse events.

Efficacy, safety and QoL analysis will be performed when last patient in has been treated for two years in the study. Kaplan-Meier method will be used to estimate the time to event analyses. The PFS, TTNT and duration of response will be calculated from the start of the first dose of study drug combination.

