This Nordic Myeloma Study Group study is a phase 2 study for advanced MM patients below 75 years of age. The main aim of this study is to assess the ORR with a new drug combination, carfilzomib + elotuzumab + dexamethasone (CAR-ELO-Dex). Even if this is not a randomized study rough comparisons can be done with earlier reports of different regimens in the same clinical situation. In addition, safety assessment is of critical importance for a new regimen. A modern concept is to study the depth of CR responses with a sensitive multiparameter flow cytometry (MFC) method for MRD assessment – an endpoint that is mostly lacking in previous studies for this patient population. We assume that treatment with this new combination of CAR + ELO + Dex will produce at least as good responses as the most efficient regimens so far used in this clinical situation, and there will be a substantial proportion of CR responses with MRD-negativity which can be regarded as an indicator of high-level treatment efficacy and which gives a good basis for comparisons of treatment efficacy between different study regimens in future.

The target population of the study is the patients who have relapsed or progressed after 1 to 3 prior treatment lines in which PI (bortezomib and/or ixazomib) and/or lenalidomide have

Helsinki University Hospital Comprehensive Cancer Center Hematology
Clinical study protocol NMSG#24/15

been included. The primary endpoint is overall response rate (ORR) while the secondary endpoints include complete remission (CR), duration of response, assessment of the depth (quality) of CR with MRD measurement by flow cytometry, estimation of PFS and time to next treatment, and evaluation of adverse events and safety.

The cycle length is 28 days.

The ELO dose is 10 mg/kg in all cycles.

CAR dose is initially (Cycle 1, day 1) 20 mg/m² weekly after which it will be increased to 56 mg/m² weekly in the first 5 patients in the first two cycles. If no safety problems occur the dose is increased to 70 mg/m² weekly for the rest of the study, and the patients after the first 5 patients will receive this dose right after the initial weekly dose of 20 mg/m²

Dexamethasone dose is 40 mg weekly throughout the study.

Drug administration schedule:

Cycles 1-2

CAR and ELO are administrated at weekly intervals on cycle days 1, 8 and 15.

Dexamethasone will be given on days 1, 8, 15 and 22.

Cycles 3-8

CAR will be administered similarly as in cycles 1-2.

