2.2 Secondary endpoints

- Complete remission
- Safety
- Minimal residual disease assessment (measured if at least VGPR response)
- Duration of response
- Time to next treatment

- Progression-free survival

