PR	$\geq 50\%$ reduction of serum M-protein and reduction in 24-h urinary M-protein by $\geq 90\%$ or to < 200 mg per 24 h In patients in whom the only measurable disease is by sFLC levels, PR is defined as a $\geq 50\%$ decrease in the difference between involved and uninvolved sFLC levels

Helsinki University Hospital Comprehensive Cancer Center Hematology
Clinical study protocol NMSG#24/15

	
If serum and urine M-protein are unmeasurable, and sFLCs are also unmeasurable, $\geq 50\%$ reduction in bone marrow plasma cells is required in place of M-protein, provided baseline percentage was $\geq 30\%$
 
In addition to the above listed criteria, if present at baseline, a $\geq 50\%$ reduction in the size of soft tissue plasmacytomas is also required

SD ^d	Not meeting criteria for CR, VGPR, PR or progressive disease

Abbreviations: CR, complete response; FLC, free light chain; IFE, Immunofixation; PR, partial response; SD, stable disease; sCR, stringent complete response; VGPR, very good partial response.

^a All response categories require two consecutive assessments made at anytime before the institution of any new therapy;

all categories also require no known evidence of progressive or new bone lesions if radiographic studies were performed.

^b Confirmation with repeat bone marrow examination not needed.

^c Presence/absence of clonal cells is based upon the κ/λ ratio. An abnormal κ/λ ratio by immunohistochemistry and/or immunofluorescence requires a minimum of 100 plasma cells for analysis. An abnormal ratio reflecting presence of an abnormal clone is κ/λ of $> 4:1$ or $< 1:2$.

^d not recommended for use as an indicator of response; stability of disease is best described by providing the time to progression estimates

NOTE: Once (s)CR is established, response remains (s)CR until relapse is documented.

RELAPSE CRITERIA

Relapse subcategory	Relapse criteria

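### Duration of response is timed from first dose, so each responder's duration includes the time before the response existed

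*Protocol*

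**What the plan says.** Section 9.2 states: "The PFS, TTNT and duration of response will be calculated from the start of the first dose of study drug combination". No other part of the protocol sets an origin for duration of response. The synopsis and section 2.2 ("Duration of response") only name the endpoint. Section 9.1 lists it as "Duration of responses including MRD negativity", again without an origin. Appendix 5 gives the response and relapse criteria but does not say when a duration begins.

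The timing of observations is fixed as follows:

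- Section 9.2: "Response will be assessed before each cycle".
- Synopsis: "The cycle length is 28 days".
- Table 1 and section 4.1: cycle laboratory work may be done up to 5 days before day 1 of the cycle.
- Footnote to the response table in Appendix 5: "All response categories require two consecutive assessments made at anytime before the institution of any new therapy".
- Section 9.1: MRD "will be assessed by 8-colour EuroFlow multiparameter flow cytometry if at least VGPR has been achieved".

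**The concern.** A duration of response should measure how long a response lasts once it has been reached. Timed from first dose, it also contains the interval in which the patient had not yet responded. That interval carries no risk of losing a response, since a patient has to stay progression-free through it to become a responder at all. Two consequences follow. The reported figure is always too long, never too short. And, other things equal, a slower response produces a longer reported duration, which is the opposite of what a reader would expect.

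The synopsis says that "rough comparisons can be done with earlier reports of different regimens in the same clinical situation". In a single-arm trial, a duration that includes pre-response time would favour the new combination in any such comparison with a figure timed from response.

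**Working it through.** **The plan's own figures.** The protocol gives no expected duration of response and no expected time to response, so there is no stated figure to reproduce on this point. Its one design figure, the 95% interval of 53-83% around an overall response rate of 70% with N=40, is reproduced by the exact (Clopper-Pearson) interval for 28/40, which is 53.5% to 83.4%. It does not depend on the time origin.

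**Identity for each responder**, whether the duration ends in an event or in censoring:

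(end date − first dose) = (first response − first dose) + (end date − first response)

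The left side is what section 9.2 calculates. The last term is the time in response. The difference is exactly the time to response.

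**Smallest possible overstatement.** Inputs are the 28-day cycle (synopsis), assessment before each cycle (section 9.2) and laboratory work up to 5 days before day 1 (Table 1, section 4.1). The assessment before cycle 1 is baseline, so the first assessment that can show a response is the one before cycle 2.

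- Sampled on day 1 of cycle 2: 28 days after first dose; 28 / 30.4375 = 0.92 months.
- Sampled 5 days earlier: 28 − 5 = 23 days; 23 / 30.4375 = 0.76 months.

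**Overstatement if first response comes after one or two cycles (assumption).** One cycle is 0.92 months; two cycles are 56 / 30.4375 = 1.84 months. Relative to the median durations cited in section 1.4.1:

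- Against 10.3 months: 0.92 / 10.3 = 8.9%; 1.84 / 10.3 = 17.9%.
- Against 20.7 months: 0.92 / 20.7 = 4.4%; 1.84 / 20.7 = 8.9%.

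These two medians serve only as a scale.

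**Effect on the Kaplan-Meier median.** The identity is exact for each patient. The median moves by about the typical time to response, not exactly by it. A simulation without censoring checked this. It assumed exponential durations and a first response after 1, 2, 3, 4, 5 or 6 cycles with probabilities 0.45, 0.25, 0.12, 0.08, 0.05 and 0.05, which gives a median time to response of 1.8 months and a mean of 2.0. A true median duration of 12.0 months became 14.0, and one of 18.0 became 20.1.

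**MRD negativity.** Section 9.1 puts it inside the duration endpoint and gives it no origin of its own. MRD is measured only once a very good partial response has been reached, so it cannot have been observed as negative on study at first dose. The size of the shift depends on when negativity is first found, which the protocol does not indicate, so no figure is given here.

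**The case against.** The strongest reply is that little depends on this endpoint. Duration of response is one of six secondary endpoints in an uncontrolled pilot. No test, threshold or sample size uses it, no treatment contrast is biased, and the origin is openly stated. All of that stands, and it limits the severity. It does not make the origin right. Nor can the matter be left to an analysis plan: the protocol has fixed the origin, and a plan that used another would contradict it.

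Some stronger readings are tempting but are not supported:

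- A reader might infer that the result cannot be compared with the cited 20.7 and 10.3 months. The protocol does not say from what point those figures were timed, so this cannot be established from the document.
- A reader might infer that the protocol expressly times MRD negativity from first dose, with a bias of many months. Section 9.2 names only PFS, TTNT and duration of response. The link to MRD comes from the wording of section 9.1 and is an inference, and any size would be assumed.
- A reader might put the minimum overstatement at a full cycle. The 5-day laboratory window lowers it to about 23 days.
- A reader might say that the endpoint is simply PFS in responders. That holds if the duration ends at the same events as PFS, but the protocol states only where it starts.

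**Conclusion.** The point holds for duration of response. Section 9.2 sets an origin at which the measured state cannot exist, and nothing else in the protocol overrides it. The direction is certain: upward, by each responder's time to response. The minimum of about 0.8 to 0.9 months follows from the assessment schedule. The range of 0.9 to 1.8 months rests on an assumed first response after one or two cycles, and its percentage size rests on true medians close to those the protocol cites. For MRD negativity the conclusion is weaker: no separate origin is given, and by inference the same rule would be applied. A reader might take this as a threat to the trial's main conclusion. It is not, because the overall response rate, PFS and TTNT do not change. It is a correction to one secondary endpoint, worth making because it is simple and because the results are meant to be set beside earlier reports.

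**What to change.** Split the sentence in section 9.2:

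- PFS and TTNT: keep first dose as the origin.
- Duration of response: in responders, from the date of the first assessment showing partial response or better, provided it is later confirmed, to progression or death. Naming the first of the two consecutive assessments avoids a dispute over which one starts the clock.
- Duration of MRD negativity: from the first MRD-negative sample.

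The cost is a small change of wording. Response is already assessed before every cycle, so no visit or sample is added. The reported duration of response will be somewhat shorter. For MRD negativity the new origin does not cure a separate limit: marrow is taken at very good partial or complete response, repeated, and then roughly annually (Table 1, section 6.6), so the date on which negativity is lost will be only as precise as that sampling. The report should say so.
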